5.1.2. Secondary outcomes

Differences in the parameters set below will be calculated for each patient and summarised by mean and standard deviations. Potential differences between patients receiving treatment within and outside treatment schedule will also be explored, if required.

- T cell responses to C19-A3 GNP as determined by changes from baseline of interferon gamma and IL-10 ELISPOT responses to this peptide in blood following treatment at weeks 0, 9 and 14.
- T cell responses to C19-A3 GNP as determined by changes from baseline of interferon gamma and IL-10 ELISPOT responses to this peptide in

draining axillary lymph node before treatment and following the last treatment administration (four aspirations: before and after visit 1 and visit 3)

- Changes in additional immunological biomarkers (e.g. flow cytometry profiles, T reg assays, autoantibodies, beta cell and T cell free DNA markers) from baseline at week 0, 9 and 14.
- Effects on residual insulin requirement and c-peptide secretion at week 14 as compared to baseline as assessed by secreted C peptide AUC after a mixed meal tolerance test and a stimulated urine c-peptide test.
- Effects on glycaemic control assessed by blood sugar profiles and HbA1c at week 14 as compared to baseline
- Scores on quality of life and diabetes self-management (week 0 and week 14).

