## **14 SAMPLE SIZE**

The single group study provides 8 patients on active treatment from whom it will be possible to collect safety data. This is considered optimal to achieve sufficient data to inform future study designs and on which to base future sample size calculations.

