## **15 PLANNED ANALYSIS**

### **15.1 Final**

Data cleaning and preparation process will be carried out prior to analysis.

All patients enrolled will be followed up and included unless they withdrew from the study before the administration of the first dose. An intention to treat analysis will be carried out. Per protocol analyses may also be carried out alongside the intention to treat analysis if necessary. The analyses will mostly consist of tables of data such as mean values (or geometric means if the data is log normal) together with standard deviations and ranges. For data such as scores, medians, and ranges may be used instead, and binary outcome variables will use percentages. Comparisons against baseline will be made using Student's t-tests for paired and unpaired samples; Mann-Whitney U test; Wilcoxon matched pairs test; p values <0.05 will be considered significant.

Since the primary aim of the study is to provide patient safety data and guide the development of an antigen specific immunotherapy programme, it may be a requirement for strategic planning of subsequent stages of clinical study development, that early analysis of trial data is conducted.

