3.3. Analysis populations

- Intention to treat population
All patients enrolled in the study
- Per protocol population
Patients receiving all three injections

4. Statistical Principle

The sample has not been powered to detect significant differences before and after treatments. Data will be analysed by simple descriptive statistics.

All patients enrolled will be followed up and included unless they withdrew from the study before the administration of the first dose. An intention to treat analysis will be carried out. Per protocol analyses may also be carried out alongside the intention to treat analysis if necessary.

Adherence to the intervention will be assessed by missed dose (protocol violation) and delayed / missed followup visits (protocol deviation).

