5.1. Analysis of outcomes

5.1.1. Primary outcome

Assessment of the safety of C19-A3 GNP administration in terms of adverse events at the dose used is the primary outcome. This includes general safety concerns, induction of hypersensitivity and exacerbation of β -cell specific autoimmunity with accelerated β -cell loss. All enrolled patients will be included in the following analysis.

General Safety

To address general safety concerns at screening and 0, 4, 8 and 14 weeks a physical examination will be conducted. A review of AEs will be performed at all visits according to seriousness, causality and expectedness. Types of AEs, body systems involved and outcomes of the AE will be categorised and analysed by incidence per person dose used. All AEs will be collated

Hypersensitivity

Patients will be observed for local and systemic reactions post injection. Number of local reactions will be analysed by incidence per person dose used, size of the erythema note and time taken for erythema note size to be reduced to < 1 cm will be analysed by mean and standard deviation. Systemic reactions will be analysed by incidence per person dose used. Therapies used and outcome will be counted and reported.

Exacerbation of β -cell specific autoimmunity with accelerated β -cell loss

Differences between week 0 and 14 will be calculated for each patient and summarised by mean and standard deviations for the following parameters:

- Measurement of islet cell autoantibodies (against insulin, GAD-65, IA-2 and ZnT8)
- Measurement of pro-inflammatory β -cell specific T cell responses (analytes to be defined)

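### The SAP reports every change from baseline as mean and SD only, so with about 8 patients a mean set by one of them would not be visible; add median, range and individual values

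*SAP*

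**What the plan says.** **SAP 5.1.2** has one rule for six groups of secondary outcomes (ELISPOT in blood, ELISPOT in lymph node, other immune biomarkers, insulin requirement and C-peptide, glycaemic control, questionnaire scores): "Differences in the parameters set below will be calculated for each patient and summarised by mean and standard deviations".

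**SAP 5.1.1**, in the part on beta-cell autoimmunity under the primary outcome, repeats it for autoantibodies and T cell responses: "Differences between week 0 and 14 will be calculated for each patient and summarised by mean and standard deviations".

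Neither section names a scale, transformation, median, range or per-patient display for these changes.

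**Protocol 15.1** is broader. Its tables are mostly to hold "mean values (or geometric means if the data is log normal) together with standard deviations and ranges". It adds: "For data such as scores, medians, and ranges may be used instead". It also lists paired and rank tests, ending with "Wilcoxon matched pairs test; p values <0.05 will be considered significant".

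**SAP section 4** (Statistical Principle) sets the inferential level: "The sample has not been powered to detect significant differences before and after treatments", and "Data will be analysed by simple descriptive statistics".

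**Protocol section 14** gives the size: "The single group study provides 8 patients on active treatment from whom it will be possible to collect safety data". Patients who miss a dose are replaced (SAP 4.1), so slightly more than 8 may be analysed.

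**The concern.** When an analysis is purely descriptive, the summary statistic is the whole result. The immune response is a stated secondary objective, and Protocol section 14 says the data are to inform later designs and sample sizes. A mean and SD from about 8 patients may reflect a shift in most of them or a large change in one, and these call for different next steps.

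The endpoints make this plausible. ELISPOT results are numbers of responding cells (Protocol 12.1.2), and autoantibody levels and cell-free DNA are quantities that are often right-skewed. The earlier peptide-only study induced IL-10 responses in 5 of 18 subjects at the 10 mcg dose (Protocol 3.2), so a minority of responders is the pattern to expect. The same summary is applied to the autoimmunity measures that the SAP places under the primary safety outcome.

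**Working it through.** The plan has no figure to reproduce: 8 patients is given without effect size, SD or power. The check is therefore whether mean and SD can hide a single dominant patient, and whether another summary does better.

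**1. Worked example (invented values, n = 8).**
- Baseline: 2, 3, 4, 5, 6, 8, 10, 12. Follow-up: 1.5, 2.2, 3, 4, 4.5, 6, 8, 60.
- Differences: -0.5, -0.8, -1, -1, -1.5, -2, -2, +48; sum 39.2.
- Mean = 39.2/8 = +4.9; SD = 17.4; median = -1.0; range -2.0 to +48.
- Without the last patient: -8.8/7 = -1.26, so the sign changes.
- Geometric mean ratio = exp(mean of ln(follow-up/baseline)) = exp(-0.298/8) = 0.96.

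**2. Does the SD give the patient away?** If one of 8 changes by D and the rest not at all, mean = D/8 and SD = D/√8, so SD/mean = 8/√8 = 2.83. A large SD does signal spread, but not its source. Four patients at +21.2 and four at -11.4 give mean (4 × 21.2 - 4 × 11.4)/8 = +4.9 and SD = 16.3 × √(8/7) = 17.4. These are the figures of step 1 from a quite different group. Median and range separate the two: -1.0 (-2.0 to +48) against +4.9 (-11.4 to +21.2).

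**3. How often one patient dominates.** Simulation: 100,000 trials, n = 8, log-normal values, no true change. Assumed between-patient log SD 0.5 to 1.5 and within-patient log-change SD 0.3 to 1.0. Share = max|d| / Σ|d|.

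| | Raw difference | Log ratio | Normal data |
|---|---|---|---|
| Median share of the largest patient | 33-52% | 27% | 27% |
| Largest patient supplies over half | 9-54% | not computed | 0.6% |
| Sign flips when that patient is dropped | 29-42% | 29-30% | 29% |

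The raw mean and the geometric mean ratio pointed in opposite directions in 17-32% of trials. The flip rate of 29% for normal data shows that part of the fragility comes from n = 8 alone.

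**4. Would a log scale be reliably better?** Probability that the average change has the wrong sign:

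| Assumed model | Raw mean | Log scale |
|---|---|---|
| All patients double, log SD 0.5, correlation 0.5 | <0.1% | <0.1% |
| All double, log SD 1.0, correlation 0.5 | 6% | 2.5% |
| All double, log SD 1.3, correlation 0.5 | 13% | 7% |
| All double, log SD 1.0, correlation 0.9 | 0.1% | 0.0% |
| Poisson counts, 5/18 respond five-fold, baseline mean 3 or 10 (log SD 0.5, correlation 0.5) | 5-7% | 8-13%, log(x+1) |

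In the responder model at baseline mean 3, log(x+0.1) gave about 18%. The typical geometric mean ratio moved from about 1.65 to 1.28 as the added constant went from 0.1 to 5. The log scale helps when everyone shifts and values are positive; it does worse on sign when a minority responds and counts are low.

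**5. Would a median alone do?** With response probability 5/18, expected responders are 8 × 5/18 = 2.2. P(3 or fewer) = 0.074 + 0.228 + 0.307 + 0.236 = 0.84. With three or fewer responders, the 4th and 5th ordered changes both come from non-responders. The median would then usually show little or no change.

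**The case against.** The other side has four good points.

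- **Conflict with the protocol.** A reader might infer that the SAP contradicts the protocol. It does not. The protocol's default is also the mean with SD; geometric means are conditional on log-normality, medians are permitted and not required, and no endpoint is named as log-normal. What stands is an omission without a stated reason. The range is the one item that Protocol 15.1 puts beside the mean without a condition.
- **Nothing is decided.** A reader might infer that one patient could decide a test or lower the study's power. The SAP plans no test, success rule or threshold on these endpoints, so a power comparison describes an analysis it does not contain. If one of 8 changes and the rest do not, a paired t statistic is only 1.0 (p = 0.35).
- **The log scale is no cure.** A reader might infer that all these assays should move to the log scale. Step 4 does not support this for ELISPOT: in the model closest to the documents' own response data the wrong-sign comparison reverses, and the result depends on the zero constant. Where skew is low or within-patient correlation high, the gain nearly vanishes.
- **Patient-level values exist.** SAP Appendix 2, Table 6 specifies a file per analyte by subject and visit. That is an input file, however; no displayed output is promised.

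What remains is that the planned output cannot show whether a mean change comes from one patient or several.

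**Conclusion.** The point holds as a gap in reporting. SAP 5.1.1 (beta-cell autoimmunity) and 5.1.2 give mean and SD alone for every change, and leave out the protocol's ranges, conditional geometric means and optional medians. With about 8 patients, one can set the size and sign of the reported mean, and mean with SD would not reveal it. Steps 1 and 2 show this without any distributional assumption. How often it would happen (9% to 54% of trials with one patient above half of the absolute change) rests on assumed skew, because the documents give no distribution for ELISPOT, titres, cell-free DNA or C-peptide.

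It does not follow that the safety conclusion is at risk: incidence of adverse events and of hypersensitivity reactions is counted separately and is unaffected. Nor do the documents show that a log mean or a median alone would be the right replacement. This is a cheap improvement that makes the secondary immune objective readable.

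**What to change.** In SAP 5.1.1 (beta-cell autoimmunity) and 5.1.2:

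1. Keep mean and SD. Add median, range and a plot or listing of individual patient values for every change from baseline.
2. For autoantibody levels, cell-free DNA and C-peptide, also report the geometric mean ratio to baseline where values are positive and approximately log-normal, in line with Protocol 15.1. Use the ratio, since a geometric mean of differences is undefined once a difference is negative.
3. For ELISPOT, show individual values with the raw summary. Treat any log ratio as supplementary, with the constant for zeros stated in advance and a check on how far the result depends on it.

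The cost is a few table columns and figures from data already collected, one constant to choose, and a SAP amendment circulated to the DSMB as SAP section 8 requires. It should be settled before database lock, so that the summary is not chosen after the data are seen.

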5.2. Handling of missing data

Every effort will be made by the study team to capture full data. In case of any missing data, three methods will be used to impute the missing data points: worst case imputation, last observation carried forward and, mean value of the non-missing cases. Sensitivity analysis will be carried out with the three imputed data sets and the complete case data set.

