### **10.3 Disease exacerbation**

Laboratory tests for exacerbation of  $\beta$ -cell specific autoimmunity are (i) measurement of islet cell autoantibodies (against insulin, GAD-65, IA-2 and ZnT8) at 0 and 14 weeks; and (ii) measurement of pro-inflammatory  $\beta$ -cell specific T cell responses at 0, and 14 weeks. Clinical manifestation of disease exacerbation will be monitored by measurement of secreted C-peptide AUC after MMTT and stimulated urine c-peptide at 0 and 14 weeks ; HbA1c levels (0, 4, 8 and 14 weeks.); and the record of blood sugars and insulin use at each study visit. Disease specific quality of life questionnaires including hypoglycaemia fear (HFS), treatment satisfaction DTSQ and quality of life ADDQoL will be performed at 0 and 14 weeks.

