### **12.2.3 Blood glucose variability**

Mean amplitude of glucose excursion (MAGE) will be calculated at 0 and 14 weeks using records from 72 hour CGM recordings.

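### SAP 5.2 names no main missing-data analysis, and two of its imputations distort week-14 changes: LOCF can force a change to 0 and mean imputation alters the SD. Separately, protocol 15.1 plans p<0.05 tests in a study that SAP 4 calls descriptive

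*SAP*

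**What the plan says.** For missing data, SAP 5.2 gives three methods to "impute the missing data points: worst case imputation, last observation carried forward and, mean value of the non-missing cases". It continues: "Sensitivity analysis will be carried out with the three imputed data sets and the complete case data set". Neither that section nor SAP 4 says which data set carries the main result. The intention-to-treat and per-protocol definitions in SAP 3.3 settle which patients count, not how gaps are filled. No direction or value is attached to worst case.

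The summaries that this rule feeds are changes from baseline:

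- SAP 5.1.1 (primary outcome) states "All enrolled patients will be included in the following analysis". For islet autoantibodies and pro-inflammatory T-cell responses it then says "Differences between week 0 and 14 will be calculated for each patient and summarised by mean and standard deviations".
- SAP 5.1.2 (secondary outcomes, including C-peptide) says "Differences in the parameters set below will be calculated for each patient and summarised by mean and standard deviations".

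The timing of several outcomes leaves only one value before week 14, or only pre-treatment ones:

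- Protocol 10.3: clinical exacerbation is "monitored by measurement of secreted C-peptide AUC after MMTT and stimulated urine c-peptide at 0 and 14 weeks".
- Protocol 10.3, after naming the HFS: "treatment satisfaction DTSQ and quality of life ADDQoL will be performed at 0 and 14 weeks".
- Protocol 12.2.3: MAGE "will be calculated at 0 and 14 weeks using records from 72 hour CGM recordings".
- The visit schedules in both documents place DTSQc, the change version, at visit 5 and not before.

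On testing, protocol 15.1 lists paired and unpaired t-tests, Mann-Whitney and Wilcoxon matched pairs for comparisons against baseline, with significance at p<0.05. SAP 4 says that the study is not powered for before-after differences and that analysis is descriptive.

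**The concern.** A sensitivity analysis needs a main analysis to be compared with, and here there is none. All four data sets are promised, but a reader cannot tell which mean and SD is the trial's result.

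Two of the three imputations also do little of what a sensitivity analysis should do. For an outcome measured at baseline and week 14 only, LOCF puts the baseline value in the week-14 slot, so the imputed change is no change at all. For C-peptide that leans towards no loss, on the measure that protocol 10.3 uses to look for disease exacerbation. Mean imputation adds no information and alters the SD, in a direction that depends on a choice the SAP does not state. Worst case is the only one of the three meant to protect against missed harm, and it is undefined. Protocol 12.1.2 implies the favourable direction for IL-10, IFN-γ and autoantibodies, but no imputed value is given, and other markers have no direction.

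MMTT values can plausibly go missing: protocol 6.18.1 allows the test only when fasting capillary glucose is between 3.9 and 11.1 mmol/L.

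The testing conflict is a separate matter. Unpaired tests do not suit a comparison of the same patients with their own baseline, and a significance rule does not fit a descriptive plan.

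**Working it through.** **Inputs.** The planned sample is 8 (protocol 14), with no power calculation behind it, so there is no plan figure to reproduce. Enrolment can exceed 8, because a patient who misses a dose is replaced but stays in follow-up (SAP 4.1). The documents give no missing rate, correlation or expected C-peptide loss, so those values below are assumptions. Notation: n enrolled, m missing at week 14, k = n − m observed.

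**Where LOCF gives exactly 0.** The whole week-14 assessment must be missing and the last earlier value must be pre-treatment.

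| Outcome | Last value before week 14 | LOCF change |
|---|---|---|
| MMTT C-peptide, HFS, ADDQoL, DTSQs | Visit 1 | 0 |
| Urine C-peptide | Visit 1 (also screening) | 0 |
| CGM/MAGE (protocol outcome, not named in SAP 5.1.2) | Baseline | 0 |
| DTSQc | None | Cannot be computed |
| HbA1c, blood glucose profiles, autoantibodies, blood T-cell assays | On-study sample exists | Not forced to 0 |

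A single missing MMTT sample or questionnaire item, carried forward, does not force 0 either.

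**Effect on the mean.** LOCF mean = (k × observed mean + m × 0)/n, so the factor is k/n.

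| n | m = 1 | m = 2 |
|---|---|---|
| 8 | 7/8 = 87.5% | 6/8 = 75% |
| 9 | 8/9 = 89% | 7/9 = 78% |
| 10 | 9/10 = 90% | 8/10 = 80% |

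**Effect of mean imputation on the SD, n = 8.**

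- Change imputed: imputed patients add nothing to the sum of squares, so the ratio is √((k − 1)/7). This is √(6/7) = 0.93 for m = 1 and √(5/7) = 0.85 for m = 2. The mean is unchanged.
- Week-14 value imputed and the patient's own baseline subtracted (equal SDs, correlation ρ): ratio² = [1 + ((k − 1)/7)(1 − 2ρ)] / [2(1 − ρ)]. At ρ = 0.5 this is 1 for either m. At ρ = 0.7 the ratio is 1.05 (m = 1) or 1.09 (m = 2). At ρ = 0.9 it is √(0.314/0.2) = 1.25 or √(0.429/0.2) = 1.46. A simulation of 200,000 trials gave the same values.

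**Yardstick.** Under normality, the 95% interval for an SD on 7 degrees of freedom is √(7/χ²), or 0.66 to 2.04 times the estimate.

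**If missing patients do worse.** Suppose the observed patients lose a fraction L of baseline C-peptide and the missing patients lose 2L (n = 8).

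- True mean loss: (7L + 2L)/8 = 1.125L for m = 1; (6L + 4L)/8 = 1.25L for m = 2.
- LOCF: 0.875/1.125 = 78% and 0.75/1.25 = 60% of the true loss.
- Observed cases: 1/1.125 = 89% and 1/1.25 = 80%. If all observed patients lose L, imputing the largest observed fall gives the same, so it is no bound.
- Week-14 value set to zero: (kL + m)/8 over the true loss. At L = 0.2 this is 0.300/0.225 = 133% and 0.400/0.250 = 160%. From L = 0.4 to L = 0.1 it runs from 106% to 189% (m = 1) and from 110% to 260% (m = 2).

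**The case against.** The best defence is that SAP 5.2 commits to all four data sets, complete case and worst case included, and that SAP 2.3 requires sign-off before database lock. A reader might infer that the reported result can simply be picked after the data are seen. The documents do not support that: the gap is which set is the main result, not which sets will be run. Likewise, the statement in SAP 5.1.1 about all enrolled patients does not flatly contradict a complete-case set that is one of several. It only leaves the denominator of the main table unsettled.

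A reader might also infer that the primary safety outcome is undermined. Adverse-event counts are unaffected, and exacerbation is monitored on measured values as they arise, not on end-of-trial imputations. The SAP lists C-peptide as secondary. The autoantibody and blood T-cell items in SAP 5.1.1 have a week-9 sample, so LOCF does not force them to 0. Only the SD and worst-case points reach them.

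Missing MMTTs may be few. The visit 5 window of plus or minus one week leaves room to repeat a test stopped by the glucose limit, though no retest rule is written, and that limit can exclude low or high values, so no direction of bias is established. Whether a urine C-peptide value would survive a cancelled MMTT is unclear. Table 1 has a separate post-meal row, but protocol 6.18.1 and 12.2.1 collect urine at 120 minutes of the MMTT.

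Finally, the SD effects are mostly small beside the 0.66 to 2.04 interval. That is true, but sampling error is expected and visible, whereas this distortion is built in by rule and avoidable.

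**Conclusion.** The point stands with a limited scope. SAP 5.2 has no main analysis and an undefined worst case. Its LOCF rule gives a zero change for a wholly missing week-14 MMTT or urine C-peptide, HFS, ADDQoL, DTSQs or CGM assessment, and it cannot be applied to DTSQc. For 1 or 2 missing of 8, the mean change falls to 87.5% or 75% of the observed-case mean. Mean imputation moves the SD by a factor between 0.85 and 1.46, depending on an unstated choice of scale and on the correlation.

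All sizes rest on assumed numbers missing, and with complete data the section has no effect. The factor-of-two loss scenario is illustrative and has no source in the documents.

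The conflict between protocol 15.1 and SAP 4 is real and independent of missing data. This merits correction before database lock, but it is not a threat to the adverse-event findings.

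**What to change.** **SAP 5.2.**

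- Add wording such as: *The main analysis of each outcome uses observed cases, reporting the number analysed and the reason for each missing value, including an MMTT not done because of the glucose limit.*
- Delete mean-value imputation.
- Delete LOCF for outcomes whose only earlier value is pre-treatment (MMTT and urine C-peptide, CGM/MAGE, HFS, ADDQoL, DTSQs) and for DTSQc.
- Keep worst case as a labelled sensitivity analysis for the week 0 to 14 autoantibody and T-cell items in SAP 5.1.1 and for C-peptide. Name C-peptide explicitly, because the SAP classes it as secondary while protocol 10.3 uses it for exacerbation.
- Fix the direction and the imputed value for each of these outcomes before database lock, and describe the result as an extreme bound, not an estimate. The value must be able to exceed the observed falls; for C-peptide, zero or the assay limit would do.

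**SAP 5.1.1.** State that enrolled patients without a week-14 value are listed, not imputed, in the main week 0 to 14 table.

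**Protocol 15.1, separately.** Remove the p<0.05 rule and the unpaired tests for change from baseline, so that it agrees with SAP 4. The exploratory comparison of on- and off-schedule patients in SAP 5.1.2 can stay as a descriptive one.

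**Cost.** Only wording changes, and less analysis than now planned. The downside is that some tables will show fewer than all enrolled patients. Observed cases alone can still understate loss, which is why the worst-case analysis is kept.
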